## 2.2.1 Subgroup of interest

The study is stratified by :

- renal insufficiency (GFR 45-60 or >60 mL/min/1.73m^2) and/or
- diabetes mellitus (on insulin or oral glucose-lowering therapy)
- baseline HF therapy (valsartan 160 mg BID at the time of randomization)

The number of subjects per stratum and combination of strata will be summarized. An analysis for primary endpoint, including the interaction between stratum and treatment will be conducted in order to estimate the stratum related treatment effects.

# 2.3 Subject disposition, demographics and other baseline characteristics

## 2.3.1 Subject disposition

A subject disposition will be created including the total number of subjects screened, the number of subjects entering the run-in period, number of subjects completing and not completing the run-in period, the No. of subjects randomized and exposed in total and per treatment group, the No. of subjects completing not completing the treatment period in total and per treatment group. The subject disposition will also include the number of subjects included in each of the analysis sets, in total and by treatment group. In addition, a table will be created listing the number of subjects per reason for discontinuation.

The number and reasons for withdrawals and discontinuations will be listed and tabulated by treatment. Separate listings will be provided for subjects screened but not included in the study (screening failures).

A table will be made displaying the number of subjects by visit.

### 2.3.2 Demographics and other baseline characteristics

The collected demographics include Age, Sex, and Race. These demographics will be summarized using descriptive statistics and will be listed.

| Novartis | Confidential | Page 14 of 30          |
|----------|--------------|------------------------|
| SAP      |              | Study No. CLCZ696BFI03 |

Medical history will be coded using MedDRA version 20.1 and will be summarized by system organ class (SOC) and preferred term (PT). All Medical history will also be listed.

## 2.3.3 Study treatment / compliance

Study drug compliance is assessed at site and recorded in the eCRF. This information will be used to evaluate the criterion of "at least 75% of the study drug doses received" for inclusion of subjects in the PPS as described in Section 2.2. The inclusion of subjects in PPS based on this criterion and other important criteria will be decided and documented as part of the pre-analysis-review, prior to unblinding of data.

The prescribed dose levels and titrated dose levels for both screening/run-in period and randomized treatment groups are captured in the eCRF. The number of subjects according to dose level will be summarized by visit.

All drug accountability data will be listed.

## 2.3.4 Prior, concomitant and post therapies

All concomitant treatments administered during the study must be recorded on the CRF page for concomitant treatments. No other investigational treatment is allowed to be used during the study. A study subject must not participate concurrently or have participated in any other clinical drug study within 3 months prior to the first study treatment administration of this study.

All concomitant medications/therapies will be classified according to ATC level 3 group text and World Health Organization (WHO) Drug Dictionary preferred name. The medications will be classified into categories Prior, Concomitant and Post IMP based on start date and end date in relation to IMP exposure (randomized double-blinded treatment).

- Prior medications are those were end dates of the medication/therapy are strictly before date of first administration of IMP.
- Concomitant medications are those for which the period between their start dates and end dates coincide with exposure to study drug and can be further classified into:
  - Concomitant medications starting prior to first exposure of IMP having start dates strictly before first exposure of IMP and end dates on same date or after date of first administration of IMP or are ongoing.
  - Concomitant medications starting on the date of first administration of IMP or after but before or on the date of last administration of IMP
- Post medications are those for which the start dates are strictly after date of last administration of IMP

The concomitant medications will be presented in a summary table broken down on timing in relation to IMP (i.e., Prior, Concomitant and Post). Each subject will only be counted once for each medication and timing category, on a preferred name level in each period.

# 2.4 Analysis supporting primary objective(s)

# 2.4.1 **Primary endpoint(s)**

The primary endpoint is this study is change from baseline in cardiac efficiency at visit 3, after 6 weeks of stable sacubitril/valsartan or valsartan treatment.

The definition of cardiac efficiency is (LV work/gram of tissue) / Oxygen consumption. Where LV work/gram of tissue is obtained by Echocardiography as (SBP x SV x HR) / LV mass, and Oxygen consumption is obtained by Cacetate PET as tracer as a mono exponential clearance rate of Cacetate (kmono)

So, cardiac efficiency is calculated based on the following formula:

Myocardial efficiency = ((SBP x SV x HR)/LV mass)/Kmono

Where

- SBP : Systolic blood pressure during PET
- SV : Stroke volume (Echocardiography)
- HR : Heart rate
- Kmono: Mono-exponential clearance rate (11C-acetate PET- scan)
- LV mass: Left ventricular mass

# 2.4.2 Statistical hypothesis, model, and method of analysis

The study hypothesis is that short-term therapy with sacubitril/valsartan added on standard HF therapy improves cardiac efficiency in subjects with systolic HF. In order to test this, the null hypothesis is formulated as follows:

 $H_0: \mu_1=\mu_2$ 

which will be tested against the alternative hypothesis:

 $H_A\colon \mu_1\neq \mu_2$ 

where  $\mu_1$  and  $\mu_2$  are the mean values of change in cardiac efficiency in the two treatment arms, as measured by PET and echocardiography at visit 3. The null hypothesis will be tested based on a two-sided test and a significance level of 0.05.

The primary endpoint, change from baseline in cardiac efficiency after 6 weeks on stable sacubitril/valsartan or valsartan therapy, will be analyzed by an ANCOVA including treatment and stratification as independent factors and covariate adjustment for baseline

| Novartis | Confidential | Page 16 of 30          |
|----------|--------------|------------------------|
| SAP      |              | Study No. CLCZ696BFI03 |

cardiac efficiency. From this model, the within treatment group changes from baseline will be estimated using least square means, and contrasts will be set up to estimate the corresponding treatment difference (sacubitril/valsartan-valsartan) with a 95% confidence interval and p-value.

Summary statistics will be prepared for the derived Myocardial energetic efficiency by visit and its change from baseline, using discriptive statistics. In addition, Box-plots will be constructed showing the distribution of changes from baseline by treatment group.

## 2.4.3 Handling of intercurrent events

The protocol for this study did not define a primary estimand of interest and thus the implication for interpretation of study results related to the occurrence and type of intercurrent events was not considered prior to design of this study.

Section 5.8 in the CSP describes criteria for withdrawal of subjects from the study. It is stated that subject may be withdrawn from the study if his/her adherence to the study protocol is not acceptable and the following situations should result in the withdrawal of the subject, unless the investigator considers it safe for the subject to continue in the study, possibly after dose modifications of the study drug or other concomitant medication:

- persistent symptomatic hypotension after randomization;

- serum potassium > 5.2 mmol/l after randomization;

- serum creatinine > 1.5 x ULN after randomization.

The CSP does not distinguish between withdrawal from study and withdrawal from treatment which would have been important for a strict treatment policy approach.

However, the number of subjects actually withdrawing from the study is expected to be very limited, which would allow a treatment policy estimand interpretion to still be applicable.

# 2.4.4 Handling of missing values not related to intercurrent event

In case of any missing response data for the primary analysis, then the missing data will be imputed using Multiple Imputation (MI). The missing data will be imputed based on the factors (treatment and stratification) and baseline as covariate as applied in the ANCOVA for the primary analysis.

## 2.4.5 Sensitivity analyses

In addition to the derivation of the primary endpoint as stated in Section 2.4.1, an alternative formula will be used, where the viable myocardium energetic efficiency will be derived as:

Viable myocardial energetic efficiency = ((SBP x SV x HR)/LV mass) / vKmono

Where

- vKmono: Viable myocardium clearance rate

| Novartis | Confidential | Page 17 of 30          |
|----------|--------------|------------------------|
| SAP      |              | Study No. CLCZ696BFI03 |

This alternative parameter is included as a sensitivity analysis to exclude possible bias related to scar tissue in subjects with ischemic myopathy. Analyses for this parameter will be done using the same approach as is applied for the primary endpoint.

# 2.4.6 Supplementary analyses

A Per-protocol analysis is planned for the primary endpoint.

Under the assumption that the primary analysis, based on FAS which is aimed to be conducted according to the intention-to-treat (ITT) principle, would correspond approximately to a treatment policy estimand analysis, then an analysis based on the PPS, which may not be conservative and potentially biased, would be an analysis which is not reflecting the same estimand as the primary analysis and is therefore considered a supplemental analysis.

This analysis will be conducted using the same methods as applied for the analysis of the primary endpoint, although any result based on this will be considered highly exploratory. No imputations using multiple imputation will be done for the PPS analysis.

The primary endpoint will in addition to overall be summarized by strata and an exploratory ANCOVA will be done where the treatment by strata interaction will be evaluated. Based on this model, the within stratum treatment difference will be estimated.

# 2.5 Analysis supporting secondary objectives

# 2.5.1 Secondary endpoint(s)

The changes in the following cardiac and systemic hemodynamics parameters will be evaluated as exploratory secondary efficacy endpoints:

- Ejection fraction (EF)
- N-terminal prohormone brain natriuretic peptide (NT-proBNP)
- Systemic BP, evaluated in relation to PET and Echocardiography
- Systemic vascular resistance (SVR)
- Coronary Vascular Resistance
- Cardiac Oxygen Consumption (kmono)

Systemic vascular resistance (SVR) will be derived as SBP/( SV x HR) and Coronary Vascular Resistance will be derived as SBP/myocardial perfusion (measured from acetate scan using K1).

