# 2.5 Rationale of the study

Even though proven effective in terms of clinical outcomes, mechanistic data about the effects of the novel ARNI sacubitril/valsartan are needed in patients with HF and reduced EF. The clinical benefits of sacubitril/valsartan (reduced hospitalizations and improvement of symptoms) can be seen within 30 days after the onset of therapy, but the underlying functional mechanisms are not known (Hubers 2016, McMurray 2014 /N Engl J Med).

Mechanical efficiency of the heart is defined as the ratio of useful energy produced (i.e. stroke work) to the amount of oxygen consumed. Excessive oxygen consumption in relation to mechanical work, i.e. reduced efficiency of forward work, is a typical feature of the failing heart. (Knaapen 2008). Previous studies have shown that cardiac efficiency can be improved by therapies that improve symptoms and clinical outcomes in HF, including cardiac resynchronization therapy, inhibition of beta-adrenergic system and inhibition of the RAAS (Knaapen 2007). ACEIs reduce mean aortic pressure and systemic vascular resistance (SVR) (Burnier 2001). Because of the related reduction in the LV load, there is an immediate increase in stroke volume and stroke work while myocardial oxygen consumption is lowered, thereby augmenting mechanical efficiency. Decreased degradation of NPs with sacubitril/valsartan encounters natriuretic resistance in HF resulting in improved endothelial function, vasodilatation and natriuresis (Hubers 2016). However, it is not known whether these beneficial hemodynamic effects result in improved efficiency of the LV work.

Cardiac oxidative metabolism can be measured non-invasively using C-acetate PET. Changes in cardiac efficiency can be seen faster (days-to-weeks) than structural changes in LV volume (months-to-years) (Knaapen 2007, Tuunanen 2008). Our hypothesis is that short-term therapy with sacubitril/valsartan added on standard HF therapy improves cardiac efficiency in patients with systolic HF.

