### 3.2 Exploratory objectives and endpoints

The exploratory objective of the study is to evaluate the effects of 6 weeks of stable sacubitril/valsartan therapy, as compared with valsartan therapy, on myocardial oxygen consumption and cardiac and systemic hemodynamics.

In order to do this, the difference in the following cardiac and systemic hemodynamic parameters will be evaluated as exploratory endpoints: EF, NT-proBNP, systemic BP, SVR, coronary vascular resistance and cardiac oxygen consumption.

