# 8.2.1 C-acetate PET- scan

Myocardial resting perfusion and oxygen consumption will be evaluated by Cacetate PET as tracer uptake ( $k_1$ ) and a mono-exponential clearance rate of Cacetate ( $k_{mono}$ ) before randomization and repeatedly on visit 3, after 6 weeks of stable sacubitril/valsartan or valsartan treatment. Resting perfusion ( $k_1$ ) will be used for calculation of myocardial vascular resistance. Efficiency of LV mechanical work will be calculated as follows:

Efficiency = (LV work/gram of tissue) / Oxygen consumption

PET-imaging will be performed using a PET scanner (GE Discovery 690PET/CT) at

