# 8.3.2 Blood pressure and heart rate

BP and HR will be measured in a seated position after at least 5 min rest at all site visits for safety assessment. BP and HR will be monitored also during the imaging sessions according to separate written instructions. SVR will be calculated based on peripheral BP and cardiac output.

In case of abnormal findings, additional control assessments may be performed according to investigator's judgement.

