# 2.6.4 Other safety data

# 2.6.4.1 Vital signs

The actual values of systolic and diastolic blood presure (BP) and heart rate (HR) and their changes from baseline will be evaluated with descriptive statistics by treatment arm. There will be two separate baseline values defined for the BP and HR measurements: the first BP and HR baseline value will be the one taken on the first screening visit. The subsequent BP and HR measurements during the screening/run-in period will be compared to this. The subsequent BP and HR measurements during the double-blind treatment period will be compared to this.

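### SAP 2.5.1 derives SVR and coronary vascular resistance from systolic, not mean, pressure, so their relative change is right only if DBP/SBP stays constant

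*SAP*

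**What the plan says.** Protocol 3.2 names six exploratory endpoints: "EF, NT-proBNP, systemic BP, SVR, coronary vascular resistance and cardiac oxygen consumption". SAP 2.5.1 gives the derivation of the two resistances: "Systemic vascular resistance (SVR) will be derived as SBP/( SV x HR) and Coronary Vascular Resistance will be derived as SBP/myocardial perfusion", with perfusion taken as K1 from the acetate scan. SBP is not loose shorthand for blood pressure, because SAP 2.4.1 defines it for the primary endpoint: "SBP : Systolic blood pressure during PET".

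The protocol is less specific. Section 8.3.2 says "SVR will be calculated based on peripheral BP and cardiac output", without naming the pressure. Section 8.2.1 says that resting perfusion (k1) "will be used for calculation of myocardial vascular resistance", again with no pressure term. The choice of systolic pressure is therefore the SAP's own. The SAP gives no reason for it, and neither SAP section 4 (changes to protocol-specified analyses) nor the SAP addendum revisits it.

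Under SAP 2.5.2 each of these endpoints gets an ANCOVA on change from baseline, with a treatment difference, 95% confidence interval and p-value. SAP 2.5.3 treats the secondary endpoints as exploratory.

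**The concern.** Vascular resistance is mean pressure divided by mean flow. Systolic pressure is mean pressure plus a part that depends on pulse pressure. A ratio of systolic pressure to flow can therefore move when resistance does not, and can stay still when resistance moves.

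Two results in the study report will carry the name resistance, each with an interval and a p-value, and readers will take them as such. If the relation between diastolic and systolic pressure changes during treatment, the reported change can have the wrong size or the wrong sign. Systolic pressure is also the only pressure term in both formulas, so a shift in diastolic pressure alone leaves no trace in either endpoint.

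**Working it through.** The plan states no expected value, variance or effect for either resistance, so there is no figure of its own to reproduce. The 27 per arm in SAP section 3 concerns cardiac efficiency and does not enter here.

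**Inputs**

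- Formulas: SBP/(SV x HR) and SBP/K1 perfusion (SAP 2.5.1).
- Systolic range at randomization: 110-160 mmHg (protocol 5.3).
- Diastolic pressures and all before/after pairs: assumptions, because the documents give none. Diastolic pressure is taken over 60-100 mmHg.
- MAP = DBP + (SBP - DBP)/3. This is the usual approximation and is not taken from the documents.

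**Step 1: level.** Write r = DBP/SBP. Then MAP = SBP x (1 + 2r)/3, so SBP/MAP = 3/(1 + 2r).

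- 125/75: r = 0.60, and 3/2.2 = 1.36.
- Lowest on the assumed grid, 110/100: MAP = 103.3, ratio 1.06.
- Highest, 160/60: MAP = 93.3, ratio 1.71.

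**Step 2: relative change.** Let r1 and r2 be the ratio at baseline and at visit 3. The visit 3/baseline ratio of the systolic index equals that of the MAP index multiplied by (1 + 2 r1)/(1 + 2 r2). The flow term (SV x HR, or K1) is the same in both indices and cancels, so one factor serves both endpoints. The factor is 1 only if r1 = r2.

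In full for 125/75 to 120/68 at unchanged flow: SBP 120/125 = 0.960, or -4.0%. MAP goes from 91.67 to 85.33, a ratio of 0.931, or -6.9%. The factor is 2.2/2.133 = 1.031, and 0.931 x 1.031 = 0.960, as it should be.

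| From | To | SBP-based change | MAP-based change | Factor |
|---|---|---|---|---|
| 125/75 | 115/69 | -8.0% | -8.0% | 1.000 |
| 125/75 | 120/68 | -4.0% | -6.9% | 1.031 |
| 130/75 | 118/74 | -9.2% | -5.0% | 0.955 |
| 125/75 | 127/68 | +1.6% | -4.4% | 1.062 |

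The first row keeps r at 0.60 and shows no error. The others show a fall understated, a fall overstated and a sign reversed. More generally, for r1 between 0.55 and 0.65, a shift in r of 0.03 to 0.05 in either direction gives a relative error of about 2.5% to 5%.

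**Step 3: what reaches the treatment contrast.** A factor SBP/MAP common to all patients and both visits multiplies the estimate and its standard error alike, so the sign, the relative size and the p-value are unchanged. If r shifts by the same factor in both arms, that factor cancels from the ratio of the arms' relative changes. The contrast in relative change is distorted only if r shifts differently by arm.

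**Step 4: venous pressure.** MAP/flow neglects downstream pressure. For 125/75 to 115/75 at unchanged flow, subtracting an assumed, unchanged venous pressure of 0, 5 or 10 mmHg gives -3.6%, -3.8% or -4.1%. The systolic index gives -8.0%. In this example, neglecting venous pressure costs far less than using systolic pressure.

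**The case against.** The strongest case against is that this is a labelling matter. The endpoints are exploratory, the formula is prespecified and open, and the tables report blood pressure, stroke volume, cardiac output and resting perfusion separately. The addendum adds ANCOVAs for the last three. A reader can largely see what drives a change in the ratio. When DBP/SBP is stable, the index tracks resistance proportionally, so it would be too strong to say that it does not measure resistance at all. All of this stands, and it limits the weight of the point.

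Feasibility is also a fair objection. SAP 2.4.1 names only systolic pressure during PET, and for imaging pressures protocol 8.3.2 says only "BP and HR will be monitored also during the imaging sessions according to separate written instructions". The diastolic values known to exist are the seated vital signs, which are a different measurement. The fix needs a fallback for this reason.

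Several stronger readings are tempting, and the documents do not support them:

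- **That the SAP contradicts the protocol.** Peripheral pressure does not exclude systolic pressure. Protocol 2.5 lists mean aortic pressure and SVR side by side as things ACE inhibitors reduce, but it does not define how SVR is calculated.
- **That the drug is expected to raise stroke volume, so DBP/SBP must shift.** Protocol 2.5 describes the stroke-volume rise for ACE inhibitors. For sacubitril/valsartan it names endothelial function, vasodilatation and natriuresis.
- **That the exploratory objective is to explain a change in efficiency.** Protocol 3.2 only sets out to evaluate effects on oxygen consumption and haemodynamics. Mechanism is the stated purpose of the biomarkers (protocol 8.2.3).

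**Conclusion.** The point holds as a correctable choice of derivation. Following SAP 2.5.1 exactly yields two ratios named as resistances whose relative change matches the MAP-based one only if DBP/SBP is constant. In the assumed examples the discrepancy runs from 4.2 percentage points too low (-9.2% against -5.0%) to 6.0 too high (+1.6% against -4.4%), with sign reversal possible.

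A reader might infer that the treatment comparison is biased, or that the 36% inflation at 125/75 is the size of that bias. Neither follows. A constant inflation is a change of scale, and a distorted contrast in relative change needs DBP/SBP to shift differently by arm. The documents contain no data on that, so the actual error is unknown and may be small.

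The conclusion rests on the general definition of resistance, the one-third approximation for MAP and assumed pressures. The primary analysis and sample size are not affected.

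**What to change.** In SAP 2.5.1:

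- Derive SVR as MAP/(SV x HR) and coronary vascular resistance as MAP/K1 perfusion, with MAP = DBP + (SBP - DBP)/3.
- Name the imaging session that supplies the pressures. The present sentence does not: SAP 2.4.1 uses systolic pressure during PET, while the addendum's LV work uses the echocardiography value.
- State that venous pressure is neglected.
- Keep the SBP-based version as a supportive index, labelled as systolic.

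If diastolic pressure was not recorded at imaging, rename both endpoints as systolic-pressure-to-flow indices in the SAP, tables and report, and do not interpret them as resistance.

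The cost is a change in derivation code, a line in the SAP or a further addendum, and supportive tables for the systolic version. The main drawback is that the preferred option depends on diastolic pressure having been captured at imaging, which the documents leave open.

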# 2.5.2 Statistical hypothesis, model, and method of analysis

The change from baseline in these parameters after 6 weeks on stable sacubitril/valsartan or valsartan therapy will be analyzed by an ANCOVA including treatment and stratification as

| Novartis | Confidential | Page 18 of 30          |
|----------|--------------|------------------------|
| SAP      |              | Study No. CLCZ696BFI03 |

independent factors and covariate adjustment for baseline cardiac efficiency. From this model, the within treatment group changes will be estimated by least square means and the corresponding treatment difference (sacubitril/valsartan-valsartan) will be calculated with a 95% confidence interval and p-value.

Descriptive statistics will be provided for these secondary endpoints by treatment arm including levels at each visit and change from baseline.

